2. LIST OF ABBREVIATIONS

AIDS: Acquired immunodeficiency syndrome
ART: Antiretroviral therapy
CAB-LA: Long-Acting Cabotegravir
CE: Cost-effectiveness
CHR: Committee on Human Research
CHV: Community health volunteer
CRF: Case report form
CVD: Cardiovascular disease
DALYs: Disability-adjusted life years
DM: Diabetes mellitus
DSMB: Data Safety Monitoring Board
ELA: Empowerment and Livelihood for Adolescents
FTE: Full-time equivalent
FGD: Focus group discussion
GPS: Global positioning system
HIV: Human immunodeficiency virus
HSV: Herpes simplex virus
HTN: Hypertension
IDI: In-depth interview
IPV: Intimate partner violence
IRB: Institutional Review Board
KEMRI: Kenya Medical Research Institute
MoH: Ministry of Health
MTCT: Mother-to-child HIV Transmission
NASCOP: National AIDS and STI Control Programme
PEP: Post-exposure prophylaxis
PEth: Phosphatidylethanol
PRECEDE: Predisposing, Reinforcing, and Enabling Constructs in Educational Diagnosis and Evaluation
PrEP: Pre-exposure prophylaxis
SAP: Statistical analysis plan
RE-AIM: Reach, Effectiveness, Adoption, Implementation and Maintenance
SEARCH: Sustainable East Africa Research in Community Health
SOMREC: Makerere University School of Medicine - Research and Ethics Committee
SOPs: Standard Operating Procedures
SSA: Sub-Saharan Africa
STI: Sexually-transmitted infections
TB: Tuberculosis
TDF/FTC: Tenofovir disoproxil fumarate/Emtricitabine

TMLE: Targeted maximum likelihood estimation

TFV: Tenofovir analyte

UCSF: University of California, San Francisco

UNCST: Uganda National Council for Science and Technology

VMMC: Voluntary medical male circumcision

VHT: Village health team. This term (Uganda) used in protocol refers to equivalent CHV
(community health volunteer)

3. PROTOCOL SUMMARY

Title: Extension of SEARCH SAPPHIRE Dynamic Choice Prevention Study

The Extension of SEARCH SAPPHIRE Dynamic Choice Prevention Study is a continuation of the 3 ongoing SEARCH SAPPHIRE Dynamic Choice Prevention randomized trials. The parent SEARCH SAPPHIRE Dynamic Prevention intervention studies were initiated in 2021, and were testing the hypothesis that a patient centered HIV Dynamic choice intervention would increase HIV biomedical prevention time in persons at risk for HIV infection.

The trial is being conducted in 3 settings; outpatient clinics, antenatal/family planning clinics, and via VHT workers in community households. The dynamic choice intervention includes counseling on and services of PrEP/PEP, choice of service location (e.g. clinic, household, community, phone), HIV testing options (including rapid or self-test provision), option for longer (e.g. 3 month) supply of PrEP, provision of a clinical officer's or nurse's mobile telephone number for immediate PEP starts any day of the week, routine assessment of barriers to initiation or adherence to PrEP/PEP, including the offer of personalized potential solutions such as choice of in-clinic or offsite service delivery, psychologic supports for traumatic experiences, and offer of concurrent, additional health or prevention related services. These services are integrated into Uganda and Kenya Ministry of Health (MoH) guidelines driven services for PrEP/PEP, augmenting local standard care procedures for the prevention of HIV. In both arms, participants have access to standard prevention offerings and will have study visits every 24 weeks for up to 3 years for HIV testing and outcomes measurement (including PrEP/PEP adherence assessment via small hair sample).

This extension protocol is a continuation of the 3 Dynamic Prevention Randomized studies for a 48 week follow up period following re-consent, with the addition of Cabotegravir (CAB-LA) as one of the dynamic choice biomedical options for intervention participants. CAB-LA is a new prevention intervention that requires injections every 8-weeks, rather than daily pill intake. CAB-LA offers an option for HIV prevention that does not require daily pills. In two head-to-head comparison studies that randomized persons to either CAB-LA or Tenofovir daily, HIV infections were reduced by over 50% in the CAB-LA arm. CAB-LA was approved in the United States in December 2021; while it is not yet approved in Uganda or Kenya, applications have been submitted and approval is expected in the coming year.

In this DCP CAB-LA Extension, persons who are currently enrolled in the DCP trials and were randomized to the intervention arm will be eligible to receive CAB-LA as one of the options in the "Dynamic prevention" model. Persons in the control arm will be eligible to receive CAB-LA if and when it is rolled out through in-country programs. Upon study approval, all participants will be offered re-consenting to continue on this study.

If CAB-LA is not available in country at the 48-week endpoint, all participants in the intervention arm will have the opportunity to continue in the study until Week 96, and participants who are currently on CAB-LA may continue through the extension. The study will end at Week 96, and by that time participants will be transitioned to in country prevention care. At 96 weeks, persons on CAB-LA will be transitioned to in country CAB-LA or to other prevention options if CAB-LA is not available. Prior to this transition, available in country

options will be assessed by the study team. HIV prevention options will be discussed with each study participant by their Week 88 visit, with a plan established for the transition to the participant's preferred prevention method in coordination with local health facilities to avoid interruption after their 96 weeks of study participation is completed.

Participants in the control arm can access biomedical HIV prevention interventions (oral PrEP, PEP) through the local health clinics. They will have access to CAB LA when it becomes available through the Ministry of Health. Participants in the intervention arm will have access to PrEP, PEP + CAB LA with the additional structured dynamic choice support described above. Intervention participants that choose not to use CAB-LA will continue on a quarterly study visit schedule, per the standard DCP Intervention study schedule. Intervention participants that choose CAB-LA will be seen once every 4 weeks for the first two injections, then every 8-weeks for injections and study visits. Should participants stop CAB-LA, they will revert to the quarterly DCP visit schedule. All participants will be seen for mid-point and end-point visits every 24 weeks.

A subset of participants that use CAB-LA (up to 40) will be asked to complete an in-depth-interview and all participants will take a survey at Weeks 0, 24, and 48 (or at CAB-LA discontinuation) for researchers to better understand participant's experience with CAB-LA and to improve delivery as it becomes more widely available. A subset of 10 providers will also be asked to complete an in-depth interview and all providers will complete surveys at their Weeks 0, 24, and 48 of administering CAB-LA. These interviews and surveys will help researchers understand better ways to deliver CAB-LA, as it becomes more widely available. Participants that seroconvert (acquire HIV during the trial) will also be asked to participate in an in-depth interview, as it will help researchers understand transmission and ways to improve DCP delivery in future implementation.

There is limited safety information available about CAB-LA use during pregnancy or breastfeeding. In the HPTN 084 trial (Phase 3 safety and efficacy trial of injectable cabotegravir compared with TDF-FTC for HIV prevention in HIV-uninfected women), the 63 women who became pregnant while taking CAB-LA had no birth defects. Given this precedent, participants will not be allowed to begin CAB-LA while pregnant, but may continue CAB-LA if they become pregnant or are breastfeeding. Participants will be explained the risks and benefits of CAB-LA during pregnancy or breastfeeding prior to enrolling in the study. Participants that become pregnant will be provided detailed information on the risks and benefits of continuing CAB LA and asked to sign a separate consent form, asking that the study team follow her, for informational purposes only, for up to 8 weeks post-partum to ascertain the outcome of the pregnancy. The pregnancy follow-up is for health monitoring of the mother and infant, as well as contributing to the global knowledge base of pregnancy and CAB-LA use.

The overall purpose of this extension is to 1) Determine if adding the option of CAB-LA as a prevention choice using a patient-centered HIV prevention delivery model increases prevention coverage (i.e. proportion of time that is covered by a biomedical prevention option, such as PrEP or PEP) compared to the standard-of-care in 3 ongoing randomized trials of Dynamic Choice Prevention in rural Uganda and Kenya; and, 2) Conduct a hybrid implementation study (Primary Objective Clinical and Secondary Objective Implementation) focusing on initial implementation

of a patient-centered model for CAB-LA using the RE-AIM evaluation framework among persons randomized to the intervention arm

4. INTRODUCTION

4.1 Background

SEARCH SAPPHIRE is an ongoing, NIH-funded study that is testing multi-disease and multi-sector interventions aimed at reducing HIV burden and improving health in rural Uganda and Kenya. Phase A is a portfolio of randomized prevention and treatment implementation studies that will inform a population-level study in Phase B.

HIV incidence in Sub-Saharan Africa (SSA) remains well above global elimination targets.¹ Despite an increasingly large, evidence-based toolkit to prevent HIV transmission, there were over 1 million new HIV infections in SSA in 2018.¹ We know from SEARCH² and three other recent SSA population-level studies³⁻⁵ that reaching (and exceeding) the UNAIDS 2020 population-level viral suppression target of 73%⁶ is insufficient to achieve epidemic control (**Table 1**). We also know that key sub-populations, in particular youth,^{4, 7-10} men,^{2, 4, 10-12} mobile populations,¹³⁻¹⁵ and persons with heavy alcohol use^{16, 17} continue to fall short of viral suppression targets, putting them at higher risk for HIV complications, mortality, and onward HIV transmission. Finally, pre-exposure prophylaxis (PrEP), an intervention that has reduced incidence in affected populations in some areas where high rates of viral suppression were already present,^{18, 19} has not been effectively deployed in high risk populations (such as young women) in SSA.^{20, 21} To achieve control of the HIV epidemic and mitigate its consequences, we need new and scalable interventions to improve delivery of prevention and treatment to vital segments of the population that contribute to persistence of new infections. We describe below why previous approaches that were effective for the majority of people in the ART roll-out do not work for subsets of these “persistent-driver” populations, our proposed solutions, and how a multi-component intervention trial can effectively inform stakeholders on programming and resource allocation to accelerate reductions in HIV incidence.

HIV prevention services that offer choice of delivery options (PrEP, CAB-LA, & PEP) and flexibility in their use and location of delivery over time allow for a dynamic, patient-centered model of prevention. This approach is responsive to the reality of an individual’s changing needs, thereby facilitating continued engagement. In SEARCH, PrEP use declined over time in spite of initial enthusiasm and uptake by early adopters²². In multiple settings, poor adherence to PrEP remains its Achilles’ heel.^{23,24} Rather than presenting PrEP in a similar framework to ART (i.e. lifelong use with 100% adherence for efficacy with delivery at HIV clinic), approaches that incorporate flexibility in choice and delivery location, akin to contraception options for women in developed countries, may prove more successful. Indeed, over the past four decades, increased choice in contraception and flexibility in access have been directly associated with increased use.^{25,26} Framing prevention in the context of healthy choices, rather than an assessment of risk, may also reduce the association of PrEP with “risky” behavior or promiscuity. Offering PEP – an event-driven option that does not require accurate prediction of risk before a potential HIV exposure (akin to a “morning after” pill), and which additionally provides protection for those with less sexual agency – is a critical innovation in flexible access to prevention services. PEP can also act as a “gateway” to PrEP or CAB-LA and other prevention modalities, providing

infrastructure to add new prevention options as they become available (e.g. the PrEP vaginal ring^{27,28}).

In the HPTN 084 superiority trial there was an 88% reduction in HIV infections in the CAB-LA arm compared to TDF/FTC, with a study population (3,224 participants) of cisgender women, aged 18-45, in Sub-Saharan Africa, including Uganda. Amongst participants that became pregnant, no congenital abnormalities were reported, with more data on pregnancy and infant outcomes expected from the HPTN 084 open-label study.

This extension describes a 48-week extension of 3 ongoing randomized trials in SEARCH Phase A studying a patient-centered “Dynamic Choice Prevention” (DCP) implementation strategy for delivering existing evidence-based biomedical prevention interventions vs. standard of care (SOC). The Dynamic prevention model offers participants choices on prevention modality on an ongoing basis: oral PrEP, or oral PEP, and the option to switch between products. The trials are being conducted in 3 settings: antenatal (ANC) clinics, the outpatient department (primary care clinics), and in rural community settings in Western Uganda and Kenya. All clinic and village health team staff (i.e., Clinical Officers, nurses, coordinators, health workers) are trained and equipped for HIV prevention care in the clinical setting, appropriate to their role.

In this extension study, participants in the intervention and control arms are reconsented and remain in their initial randomized arm. Persons in the intervention arms who remain HIV negative will be offered CAB-LA as an additional biomedical prevention option, if eligible. CAB-LA will be delivered at health clinics. The primary 48-week endpoint for this extension is proportion of time covered by a biomedical prevention product. As of May 9, 2022, a total of 1213 HIV-negative persons aged 15 years and older and at risk for HIV acquisition were enrolled in the studies. (Table 1). New participants are currently being enrolled in the original SEARCH SAPPHIRE DCP trials to replace those participants who have moved or have been unable to continue in the DCP study. The total number of participants in the study eligible for CAB-LA will not exceed the 593 listed in Table 1.

Table 1. Enrollment in 3 SEARCH Sapphire Dynamic Prevention Trials as of May 9, 2022

Dynamic Prevention Study	Intervention and Control, (N) Uganda	Intervention (N) Uganda	Intervention and Control, (N) Kenya	Intervention (N) Kenya	Total Enrolled (N), Intervention and Control	Total Enrolled Intervention (N)
Antenatal/SRH Clinic	200	100	201	103	401	203
Outpatient Department Clinics	201	100	201	97	402	197
Household Study Community Village Health Team (VHT)	200	83	210	110	410	193
All Trials Together	601	283	612	310	1213	593

5. POPULATION

5.1 Recruitment

The persons eligible for participation in the extension are those who were enrolled in the 3 ongoing DCP trials. Persons for the ANC study are recruited and enrolled through offering study participation at ANC clinics at government sponsored health facilities. Persons for the Outpatient department are recruited and enrolled through offering study participation at Outpatient department clinics at government sponsored health facilities. Persons for the community study are recruited via home visits by village health teams/community health workers.

5.2 Inclusion and Exclusion Criteria

Inclusion criteria for the Extension include:

- 1) Enrollment in a SEARCH Sapphire Dynamic Choice Prevention study
- 2) HIV negative at start of extension
- 3) Residing in study region

Additional inclusion criteria to access CAB-LA as a prevention option

- 1) Not pregnant at time of initial CAB-LA injection
- 2) Participant weighs at least 35kg

Additional Exclusion Criteria to access CAB-LA as a prevention option

- 1) Participant has Hepatitis B or chronic Hepatitis C Diagnosis
- 2) Participant has ALT \geq 5x ULN
- 3) Participant has clinical history of liver cirrhosis or current clinical evidence of cirrhosis or severe liver disease
- 4) Previous hypersensitivity reaction to cabotegravir
- 5) Receiving the following co-administered drugs for which significant decreases in cabotegravir plasma concentrations may occur due to uridine diphosphate glucuronosyltransferase:
 - i. Anticonvulsants: Carbamazepine, oxcarbazepine, phenobarbital, phenytoin
 - ii. Antimycobacterials: Rifampin, rifapentine
- 6) Participants with a current or anticipated need for chronic systemic anticoagulation or a history of known or suspected bleeding disorder, including a history of prolonged bleeding, except for the use of anticoagulation for deep vein thrombosis (DVT) prophylaxis (e.g., postoperative DVT prophylaxis) or the use of low dose acetylsalicylic acid (\leq 325 mg).

Study Intervention Clinic Locations:

All participating ANC and OPD clinics in the DCP trial will offer CAB-LA. For VHT/CHV communities, the nearest health facility will offer CAB-LA for all participants

- 1) In Uganda, the sites for each of the trials:

- a. OPD: Itojo Hospital, Kitagata Hospital
- b. ANC: Bwizibwera HCIV, Bushenyi HCIV
- c. VHT: Ndeja Health Center III

2) In Kenya, the sites for each of the trials:

- a. OPD: Magunga Level IV Hospital, Oyani Hospital
- b. ANC: Oyani Hospital, Sena Health Centre
- c. CHV: Sibouche Health Centre, Ogongo Sub-District Hospital

The demographic characteristics of the persons enrolled in the intervention arm of the DCP Trials as of May 9, 2022 currently who will be eligible for CAB-LA patient-centered intervention are shown in Table 2.

Table 2. Demographics of persons in intervention arm eligible for CAB-LA in extension phase of trial as of May 9, 2022.

	ANC Clinic	Outpatient Department	Community
Total Enrolled	203	197	193
Female Participants	203 (100%)	119 (60.4%)	111 (57.2%)
Age years number and %			
15-25 years	120 (56.9%)	90 (44.1%)	75 (38.9%)
26- 30	47 (22.3%)	33 (25.0%)	29 (25.4%)
31-40	35 (16.6%)	51 (16.2%)	49 (18.7%)
41-60	9 (4.3%)	26 (12.7%)	36 (15.0%)
61+	0 (0%)	4 (2.0%)	4 (2.1%)

Rationale: HIV prevention services that offer choice of prevention products (PrEP & PEP) and flexibility in their use and location of delivery over time allow for a dynamic, patient-centered model of prevention. This approach is responsive to the reality of an individual's changing needs, thereby facilitating continued engagement. CAB-LA is highly efficacious for HIV prevention that was recently approved by the US FDA based on two large, randomized trials HPTN 083 and HPTN 084. As CAB-LA is rolled out across rural sub-Saharan Africa, it is important to determine **how the addition of this option impacts prevention coverage in real-world settings** for women and men at risk for HIV. In addition, it is critical to design, evaluate, and improve patient-centered CAB-LA delivery strategies that maximize uptake and impact of this new product.

Ethical Considerations: The HPTN 084 study that showed efficacy of CAB LA for prevention included sites in both Uganda and Kenya. Applications for approval of CAB LA are under review in each of these countries. Thus, the information generated in this study on evaluating a dynamic prevention implementation strategy will be directly applicable. *During this proposed study extension, CAB LA is expected to become publicly available through Ministry of Health ("MoH") sponsored programs in both Kenya and Uganda. UCSF is developing an additional extension to 96 weeks, which will examine longer-term safety and implementation data of CAB-LA. Should there be delay in rollout of the MoH programs, participants could continue in this additional extension phase. After the endpoint of the 96-week extension is reached, participants*

will be transitioned to a standard of care regimen, via local healthcare system, based on the investigator's clinical judgment and local country guidelines.

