Grade \geq 3	Discontinue CAB-LA temporarily	Participants with Grade 3 nausea, vomiting, or diarrhea, for which an alternative etiology is not established, will discontinue CAB-LA temporarily until Grade 2 or lower and be treated symptomatically. Should condition(s) not improve to Grade \leq 2 within 7 days, the Investigator will consider temporary discontinuation or progressing to permanent discontinuation of CAB-LA.
----------------	--------------------------------	--

Liver chemistry monitoring

Liver chemistry monitoring is at the discretion of the provider and will occur at baseline and Week 24. Additional ALT measurements will be taken and Weeks 8 and 48 per provider discretion. Cabotegravir will be stopped if certain protocol specified liver event stopping criteria are met, or hepatotoxicity is suspected.

Liver Event Stopping Criteria

CAB must be stopped if any of the following Liver Event Stopping Criteria are met, or if the Investigator believes that it is in the best interests of the participant:

- ALT \geq 3xULN **AND** bilirubin \geq 2xULN
- ALT \geq 5xULN for more than 2 weeks
- ALT \geq 8xULN
- ALT \geq 3xULN (or \geq 3x baseline ALT) with symptoms of worsening of acute hepatitis or hypersensitivity such as fatigue, nausea, vomiting, right upper quadrant pain or tenderness, fever, rash or eosinophilia

Consideration should also be given to stopping CAB in any participant with aminotransferase elevations $>$ 3x ULN who cannot be monitored every 1-2 weeks.

When a Liver Event Stopping Criterion is met, the treating physician must do the following:

- **Immediately stop CAB-LA**
- If ALT \geq 3xULN **and** bilirubin \geq 2xULN, report as a serious adverse event (SAE) within **72 hours** using the SAE case report form.
- For **all** events meeting Liver Event Stopping Criteria, perform repeat liver chemistries and liver event follow up assessments (ideally within 24 hours of knowledge of the liver chemistry elevations) as described in the Follow-Up Assessment below and report to

UCSF, NIAID, and ViiV Healthcare using the Liver Event Case Report form within one week of first becoming aware of the event.

- A specialist or hepatology consultation is recommended if available.
- Monitor participants 2 times a week until liver chemistries resolve, stabilise or return to within baseline values.

Follow up Assessment following ANY Liver Stopping Event

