Make every attempt to carry out liver event follow-up assessments as described below for the laboratory tests that are available locally.

- Viral hepatitis serology, including:
- Hepatitis A immunoglobulin M (IgM) antibody;
- HBsAg and hepatitis B core antibody;
- Hepatitis C RNA;
- Hepatitis E IgM antibody.
- Cytomegalovirus IgM antibody.
- Epstein-Barr viral capsid antigen IgM antibody (or if unavailable, obtain heterophile antibody or monospot testing).
- Syphilis screening.
- Drugs of abuse screen, including alcohol. Record alcohol use on the liver event case report form if using.
- Serum acetaminophen/paracetamol levels
- Serum creatinine phosphokinase (CPK) and lactate dehydrogenase (LDH).
- Fractionate bilirubin, if total bilirubin $\geq 1.5 \times \text{ULN}$.
- Obtain complete blood count with differential to assess eosinophilia.
- Anti-nuclear antibody, anti-smooth muscle antibody, Type 1 anti-liver kidney microsomal antibodies, and quantitative total immunoglobulin G (or gamma globulins).
- Gamma glutamyl transferase (GGT), glutamate dehydrogenase (GLDH), and serum albumin
- International normalised ratio (INR)
- Liver imaging (ultrasound, magnetic resonance, or computerised tomography) and /or liver biopsy to evaluate liver disease. [A Liver Imaging and/or Liver Biopsy Case Report Form is available if required].
- Obtain history and record the appearance or worsening of clinical symptoms of liver injury, or hypersensitivity, fatigue, decreased appetite, nausea, vomiting, abdominal pain, jaundice, fever rash as relevant on the AE/SAE report form.

- Obtain history and record use of concomitant medications including acetaminophen, herbal remedies, other over the counter medications or putative hepatotoxins.

Liver-Safety- CAB-LA Restart

“Drug restart” refers to resuming study treatment in which there is a clear cause other than Drug Induced Liver Injury (DILI). For long acting agents, a restart may actually be a continuation of therapy rather than a true restart due to the timeframe between dose administration relative to decision making on allowing a restart.

Participants who meet Liver Event Stopping Criteria should NOT restart CAB-LA unless there is a compelling alternative cause for the liver chemistry abnormalities.

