“Drug restart” with CAB-LA in a participant who has a Liver Stopping Event may be permitted when liver chemistries improve to within 1.5x baseline and ALT < 3 xULN, provided the criteria set out in the Liver Safety Restart Guidelines are met. This should take into account when the next scheduled injection of CAB LA is due. If the restart criteria are not met by the time window for the next injection, consideration should be made to transitioning participants onto an alternative regimen.

If restart is **not allowed or not granted** by the Study’s Governing Body or Principal Investigator, permanently discontinue study treatment. Participants may continue participation in the study for any protocol specified follow up assessments.

Liver Safety Restart Guidelines

If a causal relationship between the liver event and CAB-LA cannot be ruled out, then CAB-LA must be permanently discontinued and the participant not restarted.

Note: Any decision regarding potential restart should take into account when the next scheduled injection of CAB LA is due. If the restart criteria below are not met by the time window for the next injection(s), consideration should be made to transitioning participants onto an alternative regimen.

CAB-LA Restart Following Transient Resolving Liver Events Not Related to CAB-LA

Restart can be considered when liver chemistries improve to within 1.5x baseline and ALT<3xULN where:

- Liver chemistries have a clear underlying cause other than drug-induced liver injury (e.g. biliary obstruction, pancreatic events, hypotension, acute viral hepatitis). Furthermore, there should be no evidence of alcoholic hepatitis or hypersensitivity, and the drug is not associated with HLA markers of liver injury.
- The participant is receiving compelling benefit and the benefit of drug restart exceeds risk. The long acting nature of CAB LA should be taken into consideration.

- Approval from the Principal Investigator and Ethics Committee or Institutional Review Board for the drug restart has been obtained.
- The participant has been provided with a clear description of the possible benefits and risks of drug restart, including the possibility of recurrent, more severe liver injury or death and the long acting nature of CAB injections.
- The participant has also provided signed informed consent specifically for the restart. Documentation of informed consent must be recorded in the study file.

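### CAB-LA eligibility has no bilirubin condition, so ALT 3 to <5x ULN with bilirubin ≥2x ULN passes the entry ALT rule although the same values on treatment are a mandatory stop

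*Protocol*

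**What the plan says.** **Entry.** Protocol section 5.2 lists three liver-related exclusions for CAB-LA: hepatitis B or chronic hepatitis C; "Participant has ALT \geq 5x ULN"; and "Participant has clinical history of liver cirrhosis or current clinical evidence of cirrhosis or severe liver disease". None uses bilirubin.

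**Stopping.** Section 20.2 states that "CAB must be stopped if any of the following Liver Event Stopping Criteria are met". The first criterion is "ALT \geq 3xULN AND bilirubin \geq 2xULN". For that combination the treating physician must also "report as a serious adverse event (SAE) within" 72 hours.

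**Restart.** Section 20.2 adds: "Participants who meet Liver Event Stopping Criteria should NOT restart CAB-LA unless there is a compelling alternative cause". For events not related to the drug, "Restart can be considered when liver chemistries improve to within 1.5x baseline and ALT<3xULN where" further conditions are met, including ethics approval and specific signed consent.

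**Laboratory schedule.** Table 6 footnote 4 requires ALT at baseline and Week 24 for all CAB-LA users, with Week 8 at the provider's discretion. Footnote 5 calls for bilirubin when ALT has risen. It gives no threshold, does not say that the result must precede dosing, and does not mention eligibility.

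**Product.** Section 10.2 provides for injection without an oral lead-in. Section 10.7 notes that residual drug may persist for 12 months or longer.

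**The concern.** Entry and stopping thresholds need not coincide, and a higher ALT limit at entry than in one of the stopping rules is not in itself an error. The difficulty is narrower. One combination of laboratory values is open to a first injection under the entry ALT rule, yet in a person already on the drug the protocol treats it as serious enough to require stopping and expedited reporting. The result that separates the two situations is bilirubin, and no eligibility rule asks for it.

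What is at stake is participant safety at the first dose. With an oral product, an abnormal result seen after the start can be met by stopping the tablets. With a long-acting injection given without a lead-in, the exposure is committed once the dose is in. The time to use a bilirubin result is therefore before that injection.

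**Working it through.** No power, sample-size or alpha figure is involved. The check compares the rules at given values, all in multiples of ULN.

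**Inputs (Protocol)**
- Entry ALT rule (5.2): passes if ALT < 5.
- Combined stop (20.2): met if ALT ≥ 3 and bilirubin ≥ 2.
- ALT-only stop for a single value (20.2): met if ALT ≥ 8.
- ALT part of the restart rule (20.2): satisfied if ALT < 3.

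**Worked case: ALT 4, bilirubin 2**
- Entry: 4 < 5, so the ALT rule is passed.
- Stop: 4 ≥ 3 and 2 ≥ 2, so the combined stop is met.
- Restart: 4 < 3 is false, so restart is not open at these values.

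**Edges of the region**

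| ALT | Bilirubin | Entry ALT rule | Combined stop | Restart (ALT part) |
|---|---|---|---|---|
| 2.9 | 2 | passes | not met | satisfied |
| 3 | 1.9 | passes | not met | fails |
| 3 | 2 | passes | met | fails |
| 4.9 | 4 | passes | met | fails |
| 5 | 2 | excluded | met | fails |

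The overlap is ALT from 3 to below 5 with bilirubin at 2 or above. On a grid of ALT 1 to 8 by bilirubin 1 to 4, every point in that region passed the entry ALT rule and met the combined stop, and none satisfied the restart limit. Isolated ALT in the same band (second row) meets no mandatory stop on the values alone.

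**Do other provisions close the overlap?**
- Exclusion 3 turns on cirrhosis or a clinical judgment of severe disease and has no laboratory limit. Section 11.1.1(h) asks for no dose change in mild or moderate hepatic impairment, so impairment short of severe is not a bar.
- Footnote 5 may prompt a bilirubin test at baseline, but it does not say what to do with the result before dosing.
- Section 19.5 asks for a consultation before injection for a grade 3 laboratory finding, and for grade 4 an evaluation that may lead to a hold. Neither is an exclusion.

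**With the proposed exclusion added.** Entry then requires ALT < 5 and not (ALT ≥ 3 with bilirubin ≥ 2). Repeating the grid, no point passes entry while meeting the combined stop or the ALT ≥ 8 stop.

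**The case against.** The best case for leaving the text alone has four parts.

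*The stopping rules are for people on the drug.* This is correct. The point claims only that the same values would require a stop on treatment, not that the stopping rule is breached at entry.

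*Clinicians would catch it.* The ALT row in Table 6 includes the baseline column and carries footnote 5, so a baseline ALT of 4x ULN may well lead to a bilirubin test. Section 19.5 then adds consultation for grade 3 findings, section 20.1 allows withholding for undue risk, and section 20.2 lets the investigator stop in the participant's interest. Leaving a rare pattern to judgment is a defensible design choice. This part largely stands, and it keeps the point minor. The documents do not reproduce the ALT and bilirubin grading cut-offs, so how many such cases section 19.5 would reach cannot be determined.

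*Restart is properly stricter than entry.* It governs re-exposure after a liver event. Its ALT limit also fails for isolated ALT of 3 to <5x ULN, which should remain eligible at entry. This stands: the restart limit supports the point, but the case rests on the mandatory stop.

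*The symptom-based stop is also not mirrored at entry.* ALT 4x ULN with hepatitis-like symptoms passes the entry ALT rule too, and the fix below does not address it. That criterion speaks of worsening symptoms and calls for clinical assessment; the combined criterion is purely numerical and easy to write as an exclusion.

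Two stronger readings are tempting. A reader might infer that the first dose would immediately generate a 72-hour SAE report. That needs a bilirubin result. If none is drawn at baseline, the next ALT is discretionary at Week 8 and required only at Week 24, so the event might surface late or not at all. A reader might also infer that dosing over an existing abnormality would cost the participant CAB-LA, because when a causal link to the drug cannot be excluded, "then CAB-LA must be permanently discontinued and the participant not restarted". The documents do not settle this: a recorded raised baseline ALT could equally support a cause that predates the drug.

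**Conclusion.** The point holds as a minor eligibility inconsistency with a safety consequence. As written, the entry ALT rule admits ALT 3 to <5x ULN with bilirubin ≥2x ULN to a first injection that cannot be withdrawn, and the remaining safeguards depend on judgment without barring the dose.

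The textual overlap is certain. Its practical size is unknown: the documents give no baseline liver chemistry distribution and no grading cut-offs. The limit of 593 participants eligible for CAB-LA (section 4.1) is the whole group with access and says nothing about how many would have this combination; few are likely to. The conclusion assumes that such a participant is not excluded for hepatitis B, chronic hepatitis C, cirrhosis or severe liver disease, and that the clinician does not defer the dose on judgment.

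Nothing here affects the primary comparison or its power. Someone deferred from CAB-LA remains in the assigned arm and in follow-up.

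**What to change.** 1. Keep the ALT ≥5x ULN exclusion and add one line to the CAB-LA exclusions in Protocol section 5.2: ALT ≥3x ULN with bilirubin ≥2x ULN at screening.
2. In Table 6 footnote 5, state that a baseline ALT ≥3x ULN requires a bilirubin result before the first injection.

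Both values must be raised for the new exclusion to apply, so isolated ALT of 3 to <5x ULN and isolated raised bilirubin stay eligible.

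The cost is one exclusion line and one footnote sentence, using a test that footnote 5 already foresees. The downside is an occasional wait for a bilirubin result, or deferral of CAB-LA for a few participants, who keep access to oral PrEP and PEP meanwhile. The SAP needs no change.
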